7.1. Discontinuation from Study Treatment

Patients are considered to have discontinued from study treatment when BOTH pembrolizumab and ramucirumab will no longer be administered.

Details regarding discontinuation due to an AE or due to pregnancy are found in Section [6.6](#), Section [8.2.1](#), and Section [8.2.1.2](#)). Patients will be discontinued from study treatment if they meet any of the following additional criteria:

- enrollment in any other clinical trial involving an IP or enrollment in any other type of medical research judged not to be scientifically or medically compatible with this study
- The patient, for any reason, requires treatment with another therapeutic agent that has been demonstrated to be effective for treatment of the study indication, discontinuation from the study occurs prior to introduction of the new agent.
- The investigator decides that the patient should be discontinued from study treatment.
- The patient requests that the patient be withdrawn from study treatment.
- The patient is significantly noncompliant with study procedures and/or treatment.
- disease progression (must be confirmed if patient is clinically stable [[Section 8.1.1.3](#)])
- Discontinuation of treatment may be considered for patients who have attained a confirmed CR that have been treated for at least 24 weeks and had at least 2 cycles of study treatments beyond the date when the initial CR was declared.

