In patients who have initial evidence of radiological PD, it is at the discretion of the treating physician whether to continue a patient on study treatment until repeat imaging is obtained. This clinical judgment decision should be based on the patient's overall clinical condition, including performance status, clinical symptoms, and laboratory data. Patients may receive study treatment while waiting for confirmation of PD if they are clinically stable as defined by the following criteria:

- absence of signs and symptoms indicating disease progression
- no decline in ECOG performance status
- absence of rapid progression of disease

- absence of progressive tumor at critical anatomical sites (for example, cord compression) requiring urgent alternative medical intervention

When feasible, patients should not be discontinued from study treatment until progression is confirmed by the second radiographic exam. This allowance to continue treatment despite initial radiologic progression takes into account the observation that some patients can have a transient tumor flare in the first few months after the start of immunotherapy, but with subsequent disease response. Patients who are deemed clinically unstable are not required to have repeat imaging for confirmation of PD.

[Table JVDF.6](#) summarizes the guidance for imaging and treatment after the first radiologic evidence of PD.

Table JVDF.6. Imaging and Treatment after First Radiologic Evidence of Progressive Disease

	Clinically Stable		Clinically Unstable	
	Imaging	Treatment	Imaging	Treatment
First radiologic evidence of PD	Repeat imaging approximately 4 weeks later at site to confirm PD	May continue study treatment at the investigator's discretion while awaiting confirmatory scan	Repeat imaging approximately 4 weeks later to confirm PD, per investigator discretion only	Discontinue treatment
Repeat scan confirms PD	No additional imaging required	Discontinue treatment	No additional imaging required	N/A
Repeat scan shows SD, PR, or CR	Continue regularly scheduled imaging assessments every 6 weeks	Continue study treatment at the investigator's discretion	Continue regularly scheduled imaging assessments every 6 weeks	May restart study treatment if condition has improved and/or clinically stable per Investigator's discretion

Abbreviations: CR = complete response; N/A = not applicable; PD = progressive disease; PR = partial response; SD = stable disease.

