Progression-free survival (PFS) is defined as the time from the date of first study treatment until the date of the first observed radiographically documented PD or death due to any cause, whichever is earlier. The censoring is taken in the following order:

- if a patient does not have a complete baseline disease assessment, then the PFS time will be censored at the enrollment date, regardless of whether or not objectively determined disease progression or death has been observed for the patient; otherwise,
- if a patient is not known to have died or have objective progression as of the data inclusion cutoff date for the analysis, the PFS time will be censored at the last complete objective progression-free disease assessment date.

TTR, DoR, DCR, and PFS will be assessed based on RECIST 1.1. Exploratory analysis of TTR, DoR, and PFS may be conducted using irRECIST.

Overall survival (OS), including 1- and 2- year survival rates, is determined from the date of first study treatment until death due to any cause. If the patient was alive at the data inclusion cutoff date for the analysis (or was lost to follow-up), OS will be censored on the last date the patient was known to be alive.

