- If a patient is not known to have died or have objective progression as of the data inclusion cutoff date for the analysis, the PFS time will be censored at the last complete objective progression-free disease assessment date.

Note. If there are multiple dates associated with 1 radiological tumor assessment, the assessment date will be set to the first date when the overall response is PD and the last date otherwise. A radiological tumor assessment is considered adequate if its response is CR, PR, SD, or PD.

PFS (day) = Date of progression / censor – date of first treatment + 1

Table JVDF.3. Rules for Determining Date of Progression or Censor for Progression-Free Survival

Rule	Situation	Date of Progression or Censor	Outcome
1	No baseline tumor assessments	Date of first treatment	Censored
2	No postbaseline assessments and no death	Date of first treatment	Censored
3	No documented progression and no death (with a postbaseline tumor assessment)	Date of last adequate tumor assessment	Censored
4	Patient lost to follow-up (or withdrew consent from study participation) before documented progression or death	Date of last adequate tumor assessment	Censored
5	Documented progression	Date of documented progression If a tumor assessment was done on multiple days, use the earliest date for that visit.	Progressed
6	Death without documented progression	Date of death	Progressed
7	Documented progression or death after missing ≥ 2 consecutive postbaseline tumor assessments	Date of last adequate tumor assessment before missed assessments or date of first treatment, whichever is later	Censored

Note: Progression-free survival and associated outcome is determined by the earliest of the dates above, if more than 1 situation applies.

Time-to-response, DoR, DCR, and PFS will be assessed based on RECIST v.1.1. Exploratory analysis of TTR, DoR, and PFS may be conducted using irRECIST.

Overall survival (OS) is defined as time from the date of first treatment to the date of death from any cause. For each patient who is not known to have died as of the data inclusion cut-off date for a particular analysis, OS will be censored for that analysis at the date of last contact prior to the data-inclusion cut-off date (contacts considered in the determination of last contact date include AE date, lesion assessment date, visit date, and last known alive date).

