5.2.1.5. Efficacy Analysis Variables (irRECIST)

For Study JVDF, RECIST v.1.1 will be adapted to account for the unique tumor response characteristics seen with treatment of pembrolizumab (irRECIST). Immune-related RECIST will be applied as detailed in the study protocol, and the resulting data will be included in the clinical database.

Immune-related objective response rate (irORR) is defined as the proportion of treated patients achieving a best overall response of PR or CR per irRECIST, particularly, the best

overall response by irRECIST closely related to confirmed response by RECIST. Immune-related ORR further captures responses after unconfirmed PD and does not require confirmation. For example:

- If the best response by RECIST v.1.1 is CR, then the best response by irRECIST is CR.
- If the best response by RECIST v.1.1 is PR, SD, or PD, the best response by irRECIST is the best response over the initial assessment (prior to PD by RECIST v.1.1) and the confirmation stage.

Overall, the best response by irRECIST should be the same or better than the best response by RECIST v.1.1 criteria. In addition, patients who do not have any postbaseline tumor response assessments for any reason are considered non-evaluable and will be included in the denominator when calculating the response rate.

[figure not shown]
Immune-related progression-free survival (irPFS) is defined as the date from the treatment started date to the time of PD assessed by irRECIST.

- If the initial PD is confirmed, then the date of immune-related (ir)PD is the initial PD date by RECIST v.1.1.
- If the initial PD is unconfirmed, then the date of irPD is the date of second PD.

[figure not shown]
Duration of response by irRECIST is defined from the date of first documented irCR or irPR (responder) to the date of irPD or the date of death due to any cause, whichever is earlier.

Graphic Example:

Scenario 1: The initial PD is confirmed at the next scan (consecutive PD). The efficacy variables by irRECIST and RECIST are the same.

Scenario 2: The initial PD is not confirmed at the next scan (non-consecutive PD). The efficacy variables by irRECIST and RECIST v.1.1 are different.

In addition, the best response after initial PD may be listed. Other efficacy analysis based on irRECIST may be performed for exploratory analysis.

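### Exploratory irPFS in SAP 5.2.1.5 leaves out death and gives no progression date for a first PD that is never rescanned

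*SAP*

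**What the plan says.** SAP 5.2.1.5 states that irPFS "is defined as the date from the treatment started date to the time of PD assessed by irRECIST". Two dating rules follow. A confirmed initial PD keeps its RECIST date. For the other case, "If the initial PD is unconfirmed, then the date of irPD is the date of second PD". The two worked scenarios cover an initial PD that the next scan confirms and one that the next scan does not confirm.

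The neighbouring definitions count death:

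- irRECIST duration of response, in the same section, runs "to the date of irPD or the date of death due to any cause, whichever is earlier".
- RECIST PFS in SAP 5.2.1.4 counts death, and rule 6 of Table JVDF.3 ("Death without documented progression") makes the date of death an event.
- Protocol 8.1.3 runs PFS "until the date of the first observed radiographically documented PD or death due to any cause, whichever is earlier".

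The protocol does not guarantee a second scan after a first PD:

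- Section 7.1 lists as a reason to stop treatment "disease progression (must be confirmed if patient is clinically stable".
- Section 8.1.1.3 says "Patients who are deemed clinically unstable are not required to have repeat imaging for confirmation of PD", and Table JVDF.6 gives, for these patients, "Repeat imaging approximately 4 weeks later to confirm PD, per investigator discretion only".
- Section 8.1.1.2 ends imaging at new anticancer treatment, withdrawal of consent or death.

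PFS by irRECIST is exploratory and optional (Protocol 8.1.3; SAP 5.2.1.4 and 5.3.10). SAP 5.3.10 lists both the initial progression and the progression by irRECIST for each patient with PD.

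**The concern.** irPFS is meant to show benefit that continues after a first RECIST PD. The patients whom the text leaves without an event are those who die without PD, and those whose first PD is never rescanned, for example because they were clinically unstable or moved to another treatment. Most of these are poor outcomes. If they leave the event count through censoring, irPFS rises above RECIST PFS with no pseudoprogression at all, and the gap can be misread as late benefit. The SAP text gives no irPFS censoring rule, so the handling is left to whoever programs the analysis.

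**Working it through.** **Does any visible text fill the gap?** The documents state no irPFS figure to reproduce, so the first check is textual.

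- Both dating rules and both scenario captions presuppose a next scan. A first PD that is never rescanned is not confirmed. If it is read as unconfirmed, it is dated at a second PD that does not exist.
- Table JVDF.3 stands under the RECIST v.1.1 heading and is not extended to irPFS.
- SAP 5.2.1.6 does not impute missing data by default; its date rules only complete partial dates. Its time-to-event note points to 5.2.1.3, the adverse-event section.
- Post-discontinuation imaging (Protocol Attachment 1, tumor assessment footnotes) is directed at patients without measured PD, so a later scan is not assured.

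**Size: inputs.** One cohort of 25 (SAP 5.1.2); scans at weeks 6, 12, 18 and 24 (Protocol 8.1.1.2); the 24-week PFS rate (SAP 5.3.10). Assumed, because the documents give no such figures: 7, 5, 4 and 3 PFS events by the four scans, so 19 in total; the number of deaths without PD and of never-rescanned PDs; and that every rescanned PD is confirmed. RECIST PFS at 24 weeks is then (25 - 19)/25 = 6/25 = 24%.

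**Formula.** Kaplan-Meier on the scan grid: S(24) = product over the four scans of (1 - confirmed PDs / number at risk). Deaths and never-rescanned PDs are censored.

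**Hand example.** Two deaths (one before week 6, one before week 12) and three never-rescanned PDs (weeks 6, 12 and 18):

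- PDs censored at the last progression-free scan: 18/23 x 13/16 x 9/12 x 6/9 = 0.318.
- PDs censored at the PD scan: 19/24 x 14/17 x 10/13 x 6/9 = 0.334.

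**All placements of the lost events among the 19.** Mean 24-week irPFS (range):

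| Deaths + never-rescanned PDs | Censored at last progression-free scan | Censored at PD scan |
|---|---|---|
| 0 + 0 | 24.0% | 24.0% |
| 2 + 0 | 27.4% (26.1-30.9%) | the same |
| 1 + 1 | 27.4% (26.1-30.9%) | 28.0% (26.4-31.5%) |
| 2 + 3 | 33.7% (30.0-42.5%) | 35.4% (30.4-44.0%) |

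For scale, true pseudoprogression in 2 or 3 patients, with their irPD after week 24, would give 8/25 = 32% or 9/25 = 36%.

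**Other base rates.** With a constant hazard and a share f of events censored at their own dates, S becomes S^(1-f). For f = 5/19 = 0.263:

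- 0.24^0.737 = 0.349 (+10.9 points)
- 0.61^0.737 = 0.695 (+8.5 points)
- 0.71^0.737 = 0.777 (+6.7 points)

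The last two bases are the 6-month PFS rates of 61% and 71% that Protocol Section 2 quotes for biliary tract cancer.

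**Direction in a single cohort.** 600 simulated 25-patient cohorts were run for each setting, on the protocol scan schedule. Underlying median PFS was 8.6 or 19.6 weeks (8.6 weeks and 4.5 months in Protocol Table JVDF.1). Shares were assumed: 10% deaths with 10% never rescanned, or 20% with 30%.

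- Censored at the event date, the literal rate was never below the reference.
- Censored at the last progression-free scan, it was below in 0 to 2.3% of cohorts.
- With the patients dropped instead, the mean difference was only -0.1 to +2.0 points.

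**Is adding death enough?** No. With three never-rescanned PDs and death counted, the 24-week rate still lies between 6/25 = 24% and 9/25 = 36%, depending on when those patients die or are censored.

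**The case against.** The strongest reply is that the death omission is a slip that no programmer would follow. The endpoint is called progression-free survival. Both documents speak of PFS using irRECIST after defining PFS with death, and the adjacent duration of response counts it. The irPFS sentence itself is garbled. This is probably right about intent, but it does not change the sentence that states the definition, and it does nothing for the undated PD.

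On the second part, the scenario caption treats an unconfirmed PD as one that the next scan failed to confirm. A never-rescanned PD then falls outside the second-PD rule, and because the protocol asks for confirmation only in stable patients, one could let an unstable patient's first PD stand. That is a sensible reading, but the SAP does not state it. The section's figures are not visible and may carry definitional content: SAP Version 3 was issued to correct the illustration for irRECIST duration of response. If they settle these cases, the text should say so too.

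The size is also open to challenge. A loss of 5 of 19 events (26%) is an assumption, and only that case resembles 2 to 3 patients with late benefit. The smaller shifts, 24% to 27-28%, lie well inside the exact binomial 90% interval for 6/25, about 11% to 42%. These points stand and limit the weight of the finding.

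**Conclusion.** As written, the irPFS definition is incomplete. It omits death, gives no date to a never-rescanned first PD, and states no censoring rule. Followed literally, with such patients censored, irPFS exceeds RECIST PFS in expectation without any pseudoprogression: 27-28% against 24% with 2 of 19 events lost, and about 34-35% with 5 of 19 lost. These figures rest on the assumed shares, the assumed 24% base and the assumption that every rescanned PD is confirmed; the shift differs at other base rates.

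A reader might infer three stronger things that the documents do not support. First, that irPFS will always be inflated: with no such cases it equals RECIST PFS under these assumptions, dropping the patients leaves a possibly small bias, and a single small cohort can go the other way. Second, that death was deliberately excluded: the surrounding definitions point to a slip. Third, that the trial's efficacy conclusions are compromised: RECIST PFS, ORR and the primary safety objective are unaffected, irPFS is exploratory and optional, and the planned listing lets any gap be traced patient by patient. Priority is low to moderate.

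**What to change.** In SAP 5.2.1.5:

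1. Define irPFS as the time from first treatment to the earlier of irPD or death from any cause.
2. Add that an initial PD with no later evaluable scan counts as irPD on the initial PD date. In the 5.3.10 listing, flag patients whose rescan was not yet due at data cutoff.
3. State that the Table JVDF.3 rules apply to irPFS, with irPD in place of documented progression.

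Under the assumptions above, the first two sentences bring the illustrative rate back to 24%. The second also supplies the irPD date that irRECIST duration of response needs.

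Clerical: the time-to-event note in SAP 5.2.1.6 should point to 5.2.1.4 and 5.2.1.5.

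The cost is three sentences, a flag in a listing already planned, and one corrected cross-reference; no new data are needed. The downside is that a first PD found within about 4 weeks before a cutoff counts as irPD before its rescan is due. This makes irPFS slightly conservative at an interim analysis, and the flag shows how many patients are affected.

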5.2.1.6. Handling of Dropouts or Missing Data

Rules for handling dropouts or missing data are listed by type of analysis alphabetically. Unless otherwise specified, observed data will be used and missing data will not be imputed or carried forward.

General rules for imputing dates related to AEs or concomitant therapy:

- Onset date of an AE or start date of a concomitant therapy:
 - If only the day is missing, the date will be set to:
 - First day of the month that the event occurred, if the onset yyyy-mm is after the yyyy-mm of first study treatment.
 - The day of the first study treatment, if the onset yyyy-mm is the same as yyyy-mm of the first study treatment.
 - If both the day and month are missing, the complete date will be set to:
 - January 1 of the year of onset, if the onset year is after the year of the first study treatment.
 - The date of the first dose, if the onset year is the same as the year of the first study treatment.

- Resolution date of an AE or end date of a concomitant therapy:
 - If only the day is missing, the date will be set to the last day of the month of the occurrence, or to the date of death if the patient died in the same month.
 - If both the day and month are missing, the date will be set to 31 December of the year of occurrence.

If a date is completely missing, then the AE will be considered treatment emergent. In case of additional therapies, the therapy will be considered concomitant.

General rule for imputing other dates: If a date variable is needed for an analysis, use the following general rule to impute incomplete date:

- If the date has no missing year and month but the day is missing, then assign Day 1 to the day
- If the date has no missing year, but has a missing month, then assign January to the month.

However, after imputation, check if the imputed date is logically consistent with other relevant date variable(s) and make appropriate correction if necessary. For example, if a visit start date was 10 May 2015 and a tumor assessment date was xx May 2015 (missing day), but it was known that it occurred after that visit, then after imputation, the tumor assessment date became 01 May 2015. In this case, the imputed tumor assessment date should be compared to the visit start date and then corrected to be the visit start date, 10 May 2015.

Safety analysis: The following rule for missing data processing will apply for safety analysis:

- Missing classifications concerning study medication relationship will be considered as related to study medication (both components).
- If the AE onset date is missing or partial, the date will be compared as far as possible with the date of first dose of study medication when determining whether or not the AE is present at baseline. In this case, the AE will be assumed to be treatment-emergent, unless there is clear evidence (through comparison of partial dates) to suggest that the AE started prior to the first dose of study medication.

Time-to-event analysis: All censored data will be accounted for using appropriate statistical methods. See Section [5.2.1.3](#) for details.

5.2.1.7. Analysis Population

Patients **entered** into the trial are those who sign the informed consent document.

Patients **enrolled** in the trial are those who have been assigned to a treatment and have received at least 1 dose of study treatment.

The **safety analysis and efficacy analysis set** will be based on all enrolled patients.

5.3. Description of Analysis

5.3.1. General Consideration

All data, including derived data, will be listed for all enrolled subjects by study phase, assigned LY3009806 dose, cohort, patient number, cycle, and time point where appropriate, unless stated otherwise in the following text or in the table shells.

In the Phase 1a part of the study, data will be summarized by assigned ramucirumab + pembrolizumab dose levels and schedules for preliminary analysis unless stated otherwise.

Note: 2 dose schedules of ramucirumab were considered for the Phase 1a part of the study. In addition, data may be summarized by the same indication and dose schedule in combination with the Phase 1b part of the study. They are:

- 2L-3L Gastric (Schedule1): Cohort A + Phase 1a patients with same indication/dose schedule/level as Cohort A
- 2L-3L Gastric (Schedule2): Cohort B + Phase 1a patients with same indication/dose schedule/level as Cohort B
- 2L-4L NSCLC: Cohort C + Phase 1a patients with same indication/dose schedule/level as Cohort C
- 2L-4L Urothelial: Cohort D + Phase 1a patients with same indication/dose schedule/level as Cohort D
- 2L-3L Gastric (total): 2L-3L Gastric Schedule 1 + 2L-3L Gastric Schedule 2

In general, continuous variables will be presented using the mean, standard deviation, median, minimum, maximum, and number of patients with an observation (n).

For categorical variables, the population size (N), the number of events, the number of subjects with events (n), and the proportion of subjects with events ($p=n/N$) are usually reported.

Additional exploratory analyses of the data will be conducted as deemed appropriate.

